6.2.3. Bone Marrow Examination

A bone marrow aspirate and biopsy are optional for all subjects at Screening. A bone marrow aspirate and biopsy must be collected for all subjects at the time of the CR/CRi confirmation visit within 12 weeks after clinical, imaging, and laboratory response criteria have been met.

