7.2. Inclusion Criteria

As of 05 Jul 2018, enrollment of new subjects into Phase 1 has been discontinued and Phase 2 will not proceed.

Subjects must satisfy the following criteria to be enrolled in the study:

1. Subjects \geq 18 years age and \leq 80 years of age at the time of signing the informed consent form.
2. Understand and voluntarily sign an informed consent form prior to any study related assessments/procedures being conducted.
3. Able to adhere to the study visit schedule and other protocol requirements.
4. Must have a documented diagnosis of CLL/SLL requiring treatment (IWCLL Guidelines for the Diagnosis and Treatment of CLL [Hallek, 2008]). In addition:
 - a. Presence of at least one clinically measurable lesion:
 - i. nodal lesion that measures \geq 1.5 cm in longest dimension (LD) and \geq 1.0 cm in longest perpendicular dimension (LPD), or
 - ii. spleen that measures \geq 14 cm in longest vertical dimension (LVD) with a minimum of 2 cm enlargement, or
 - iii. liver that measures \geq 20 cm in LVD with a minimum of 2 cm enlargement, or
 - iv. peripheral blood B lymphocyte count $>$ 5000/uL

5. Must meet the criteria for relapsed and/or refractory disease according to the IWCLL guidelines [REDACTED] to ≥ 1 prior treatment (with the exception of Arm B) and have evidence of disease progression requiring treatment at the time of study entry as follows:

a. For Arms A and C, subjects must have received either prior chemoimmunotherapy or therapy with an approved BTK inhibitor with the following exceptions:

i. Chemoimmunotherapy is not required if subjects have specific co-morbidities that preclude the use of standard chemoimmunotherapy meeting at least 1 of the following criteria;

1. CIRS ≥ 6 ;
2. Creatinine Clearance < 70 mL/min;
3. Subject is not a candidate for a chemoimmunotherapy in the opinion of investigator.

The reason for not being a candidate must be documented in the CRF.

ii. Treatment with an approved BTK inhibitor is not required if subject has contraindications or is not a candidate for such a therapy in the opinion of the investigator.

The reason for not being a candidate must be documented in the CRF.

b. For Arm B, subjects with treatment-naïve or R/R CLL must meet the following criteria:

i. Dose Escalation Phase: Subjects must not have received prior treatment with ibrutinib (or any other BTK inhibitors) and must have:

1. R/R CLL: has 17p- and/or TP53 mutation; or

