10. EFFICACY ANALYSIS

The efficacy endpoints of this study include ORR, MRD, DoR and PFS based on the International Workshop on Chronic Lymphocytic Leukemia (IWCLL) [REDACTED] with modifications [REDACTED] [REDACTED] for subjects with CLL and based on the revised International Workshop Lymphoma criteria for response assessment [REDACTED] for subjects with SLL. For subjects with CLL see [Table 3](#) for details and for subjects with SLL see [Table 4](#) for details. Lymph node responses will be assessed separately and independently of increases in blood lymphocyte counts.

Efficacy response according to the respective criteria for CLL/SLL will be formally assessed every three cycles during the first two years and every 6 cycles thereafter at the time of physical examinations until documented progression or initiation of subsequent CLL therapy. PD based on physical and/or laboratory tests at any time should be confirmed by CT scan. CR/CRI confirmation by bone marrow examination must be completed within 12 weeks after clinical criteria have been met. Furthermore, CT scans at Screening, end of Cycle 6 are mandatory (the 2nd scan is mandatory only for the affected regions with abnormal findings at baseline; Week 25 (for subjects on Arms A and C) or Week 29 (for subjects on Arm B), +4 weeks/-1 week).

Tables and listings will be provided to describe the efficacy endpoints tabulated by dose cohort and overall for each treatment arm. Efficacy analysis will include a summary of ORR, MRD, DoR and PFS.

For each subject the survival status will be provided in a listing.

In addition, a waterfall of the best percentage change from baseline sum of the product of the perpendicular diameters for multiple lesions will be provided for subjects with measurable nodal lesions at baseline. Each subject's best percent change will be represented by a bar, with a pattern specific to the dose level to which they were initially assigned to (in dose escalation phase).

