Group B	Platelet count	> 100,000/ μ L	> 100,000/ μ L or increase $\geq 50\%$ over baseline	> 100,000/ μ L or increase $\geq 50\%$ over baseline	Current platelet is < 100 x $10^9/L$ and there has been a decrease of $\geq 50\%$ from baseline secondary to CLL
	Hemoglobin	> 11.0 g/dL	> 11.0 g/dL or increase $\geq 50\%$ over baseline	> 11.0 g/dL or increase $\geq 50\%$ over baseline	The current hemoglobin is < 11 g/dL and there has been a decrease of > 2g/dL from baseline secondary to CLL
	Neutrophils	> 1500/ μ L	> 1,500/ μ L or increase $\geq 50\%$ over baseline	> 1,500/ μ L or increase $\geq 50\%$ over baseline	-

Abbreviations: ALC = absolute lymphocyte count; CLL = chronic lymphocytic leukemia; CRi = complete response with incomplete marrow recovery; IP = investigational product; LD = longest diameter; LPD = longest perpendicular diameter; LVD = longest vertical dimension; SPD = sum of the product of the perpendicular diameters for multiple lesions.

Notes:

* Complete Response (CR): all of the criteria have to be met, and subjects have to lack disease-related constitutional symptoms; Partial Response (PR) and Partial Response with Lymphocytosis (PRL): at least two of the criteria of Group A plus one of the criteria of Group B have to be met. There are two exceptions in which only 1 criterion is needed: 1) only lymphadenopathy is present at baseline (applicable to PR only); 2) only lymphadenopathy and lymphocytosis are present at baseline. In these two scenarios (applicable to PRL only), only lymphadenopathy must improve to the extent outlined in the Group A criteria in the table; Stable Disease (SD) is the absence of Progressive Disease (PD) and failure to achieve at least PR; PD: at least one of the above criteria of Group A or Group B has to be met. Lymphocytosis as a criterion for PD is not applicable to ibrutinib treated subjects and generally requires other supportive evidence of PD. Response or PD assessment of lymphadenopathy may also be based on longest diameters of the enlarged lymph nodes and the same method should be applied consistently to all lesions.

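### SAP Table 3 leaves CLL subjects whose only abnormal Group A parameter is spleen, liver or blood lymphocytes with generally no route to PR on scheduled data

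*SAP*

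**What the plan says.** Entry: Protocol 7.2, criterion 4.a, asks for "Presence of at least one clinically measurable lesion" and lists four alternatives. One is a node. The others begin "spleen that measures", "liver that measures" and "peripheral blood B lymphocyte count", with thresholds of 14 cm, 20 cm and 5000/µL. Any one of the four is sufficient.

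Response: SAP 10.1, Table 3 and its footnote *, govern CLL. Group A holds nodes, liver, spleen, blood lymphocytes and marrow; Group B holds platelets, hemoglobin and neutrophils. For PR and PRL, "at least two of the criteria of Group A plus one of the criteria of Group B have to be met". Two exceptions need one criterion only. The first applies where "only lymphadenopathy is present at baseline (applicable to PR only"; the second applies where nodes and lymphocytosis are the only findings. A subject who has not progressed and does not reach PR is SD, and SD is outside the ORR numerator.

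Marrow: Protocol 6.2.3 states "A bone marrow aspirate and biopsy are optional for all subjects at Screening". Later marrow is mandatory only at the CR/CRi confirmation visit; SAP 10.5 agrees.

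**The concern.** Three of the four ways into the study have no matching one-criterion exception. A subject with lymphocytosis only, whose count falls by more than half but stays at or above 4000/µL, meets the Table 3 PR limit for the one parameter that was abnormal. The subject is not a CR candidate, so no marrow is triggered, and the record reads SD.

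The rule is also asymmetric. PD needs one criterion from either group (with a carve-out for lymphocytosis under ibrutinib), so these subjects can progress on one parameter but not partially respond on it. Elsewhere the plan treats such a change as response: for Arm A escalation, Protocol 4.1 accepts a fall in lymphocyte count or shrinkage of measurable lesions as objective evidence.

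At stake are ORR, time to response and DoR (SAP 10.1 to 10.3), since the last two include responders only. The blood MRD sample triggered by PR (Protocol 6.2.4) would be missed as well. PFS does not depend on the split between PR and SD. The classification also has a use outside the efficacy tables: Protocol 8.2.12.1 calls certain CC-122 doses active if at least one objective response was seen in the fixed-dose cohorts.

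**Working it through.** The plan gives no figure on this point to reproduce. The check is of the rule itself, followed by the effect on ORR.

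**Step 1: entry routes against exceptions.** The Table 3 PR limits for nodes, liver, spleen and lymphocytes are all worded as decreases. A parameter that was normal at baseline therefore cannot supply the second criterion.

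| Sole abnormal Group A parameter | Eligible under 4.a | PR exception in Table 3 | PR reachable without marrow |
|---|---|---|---|
| Nodes | i | yes | yes |
| Spleen | ii | no | no |
| Liver | iii | no | no |
| Blood lymphocytes | iv | no | no |

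**Step 2: all baseline patterns.** Five Group A parameters give 2^5 − 1 = 31 non-empty sets of abnormal parameters. Take the best case: every abnormal parameter improves to the PR extent and Group B is met. Then apply the two-criterion rule with the nodes-only exception.

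- Marrow measured at baseline and again on study: 4 of 31 patterns cannot reach PR (liver only, spleen only, lymphocytes only, marrow only).
- No paired marrow: 8 of 31. The additions are marrow together with one of nodes, liver, spleen or lymphocytes. Nodes plus marrow fails only if known marrow disease takes the subject outside the nodes-only exception.

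These counts are of patterns, not of subjects, and say nothing about frequency. If any sole abnormal parameter sufficed, all 31 patterns could reach PR given the marrow data.

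**Step 3: effect on ORR.** With k affected partial responders among n subjects, ORR is lower by k/n. For k = 1:

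- Arm A, n = 20 (Protocol 7.1): 1/20 = 5.0 points.
- Fixed-dose cohort, n = 6 (Protocol 4.1): 1/6 = 16.7 points.
- Fixed-dose cohort, n = 3: 1/3 = 33.3 points.

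Illustrations with assumed responder counts and the SAP's Clopper-Pearson 95% intervals:

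- 10/20 = 50.0% (27.2 to 72.8) becomes 9/20 = 45.0% (23.1 to 68.5).
- 3/6 = 50.0% (11.8 to 88.2) becomes 2/6 = 33.3% (4.3 to 77.7).

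The point estimates move visibly, while the intervals overlap almost entirely.

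**The case against.** Much of the case on the other side stands and sets the limits of the point.

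- **PR is not strictly impossible.** A reader might infer that these subjects can only be CR, SD or PD. The marrow row of Table 3 also accepts B-lymphoid nodules, which is not worded as a change from baseline. A subject who clears clinically but shows nodules at the confirmation marrow could be PR or nPR, and both count in ORR. CR and CRi are open throughout. A subject with an optional screening marrow and a later one could also reach two criteria.
- **The entry route is not the baseline pattern.** The entry thresholds (spleen 14 cm, liver 20 cm) lie above the PR targets (12 cm and 18 cm). Someone who enters on lymphocytosis with a 13 cm spleen may still have two parameters that can improve. Affected subjects must be found from baseline values, not from the criterion ticked.
- **Arms and diagnosis.** In the PRL column, persistent lymphocytosis is itself the Group A entry, so a spleen-only or liver-only subject in Arm B may arguably reach PRL. SLL follows Table 4. The point is clearest for CLL in Arms A and C and for lymphocytosis-only subjects.
- **The waterfall plot.** It "will be provided for subjects with measurable nodal lesions at baseline". A reader might infer that the SAP expects single-parameter subjects. It does not show that: a percent change needs a non-zero baseline, and a subject without nodes may have both spleen and lymphocyte disease.
- **Unseen text.** Protocol 6.2.7 places the CLL criteria in Appendix A with modifications. That appendix is not in the text available here, so a covering exception cannot be excluded. Table 3 as given has none.
- **Late change.** Response is investigator-assessed and open-label, and enrollment has closed. Loosening PR now could only raise ORR. That argues against replacing the definition, but not against a labelled supportive analysis.

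One argument goes too far: that nothing depends on the classification because the expansion cohorts and their futility analyses are cancelled. Protocol 8.2.12.1 still uses objective response to call a dose active.

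**Conclusion.** The gap is real in the text. For CLL subjects whose sole abnormal Group A parameter is spleen, liver or blood lymphocytes, a PR-level improvement will generally be recorded as SD. Each such responder costs 1/n in ORR (5.0, 16.7 or 33.3 points at n = 20, 6 or 3) and is lost from time to response and DoR.

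A reader might go on to infer that this trial's ORR is understated by a definite amount. The documents do not support that. They give neither the number of such subjects nor their response probability, and the effect is zero if none enrolled or none partially responded. The conclusion rests on Table 3 being the operative rule, on no covering exception in Protocol Appendix A, and on a parameter normal at baseline not counting as improved. Efficacy is a secondary, descriptive objective here, so this is worth correcting but does not threaten the primary safety conclusions.

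**What to change.** Keep ORR under the current Table 3. Before database lock, prespecify a supportive ORR and DoR in which a CLL subject with exactly one abnormal Group A parameter at baseline (nodes, spleen, liver or blood lymphocytes) is PR if that parameter improves to the Table 3 extent, one Group B criterion is met and no PD criterion is met. Derive it from the CT and blood count data already collected, at the scheduled response assessments, so that a passing dip between them does not count. Report the number of such subjects by arm and dose cohort, flag them in the response listing, and check the rule against Protocol Appendix A first.

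In the same edit, reconcile the footnote: the lymphadenopathy-only exception is marked as applying to PR, but the sentence that follows describes both scenarios as applying to PRL only.

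The cost is some extra programming and a second ORR figure to explain. No new data are needed. For spleen-only and liver-only subjects the derived DoR will be coarse, because CT is mandatory only at screening and after six cycles of CC-122.

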10.2. Duration of Response (DoR)

For subjects with response as PR, nPR, PRL (applicable to Arm B only), CRi or CR, the Duration of Response (DoR) is measured from the time the response is first met until the first date that PD or death is documented. Subjects who neither progress nor die or who withdrew consent or are lost to follow-up prior to documentation of progression will be censored at the date of their last adequate response assessment. Adequate efficacy assessment encompasses protocol defined assessments of tumor lesions (lymph nodes, spleen, and liver), peripheral blood test, bone marrow assessment when indicated, and clinical assessment.

The Kaplan-Meier estimate of median DoR along with a two-sided 95% CI will be provided by dose cohort and overall for each treatment arm in a table using Safety and EE populations.

A listing of all subjects with their response and best overall response will be provided. A separate listing will also include the DoR (for subjects with response as CR, CRi, PR, nPR or PRL [PRL applicable to Arm B only], based on the criteria defined above for CLL and SLL).

10.3. Time to Response and Time to Best Overall Response

Time to Response

For subjects with response as PR, nPR, PRL (applicable to Arm B only), CRi or CR, the time to response is measured from the first dose date of any treatment to the date a response is first met (PR, nPR, PRL [applicable to Arm B only], CRi or CR). Subjects who did not have a response are not included in the analysis.

The median, mean, standard deviation, minimum and maximum of the time to response will be provided by dose cohort and overall for each treatment arm in a table using Safety and EE populations.

Time to Best Overall Response

For subjects with response as PR, nPR, PRL (applicable to Arm B only), CRi or CR, the time to best overall response is measured from the first dose date of any treatment to the date the best overall response is first met.

The best overall response is the best response amongst the following response: CR, CRi, nPR, PR and then PRL. Subjects who did not have a response are not included in the analysis.

The median, mean, standard deviation, minimum and maximum time to response will be provided by dose cohort and overall for each treatment arm in a table using Safety and EE populations.

A by-subject listing will be displayed for the time to response and time to best response for responder alongside the DoR.

10.4. Progression-Free Survival (PFS)

Progression-Free Survival (PFS) will be calculated as the time from first IP (i.e. any study drug) dose date to the first documented progression or death due to any cause during or after the treatment period, whichever occurs first. PD is determined by criteria defined in [Table 3](#) for CLL and [Table 4](#) for SLL.

A subject who has neither progressed nor died will be censored on the date of his or her last adequate tumor response assessment. Subjects without adequate baseline or post-baseline efficacy assessments will be censored on their first dose dates. [Table 5](#) summarizes the different scenarios for consideration for censoring.

Table 5: Censoring Method for Progression-Free Survival Time

Situation	Date of Progression or Censoring	Situation Outcome
No post-baseline response assessments	Date of the treatment start	Censored
Progression documented before subsequent anti-CLL/SLL therapy	Earliest of sample collection date, target and non-target lesions date for samples supported the response assessment	Events
Death before first PD and subsequent anti-CLL/SLL therapy	Date of death	Events
No progression nor death	Date of last adequate response assessment with evidence of no progression	Censored
Study discontinuation for reasons other than PD or death	Date of last adequate response assessment with evidence of no progression	Censored

New anti-CLL/SLL treatment started with no claim of progression	Date of last adequate assessment with evidence of no progression prior to the start of new anti-CLL/SLL treatment	Censored
---	---	----------

Analysis of PFS will be provided for different dose cohorts and overall by treatment arm in a table. Median and 1st quartile PFS will be estimated using Kaplan-Meier estimates and the 95% CI will be computed using the method of Klein and Moeschberger [REDACTED] with log-log transformation for each treatment arm and dose level. The number of events, subjects censored, and the Kaplan-Meier estimates of PFS rates at the time points of three, six months, one, two and three years along with the 95% CI of rate estimates, will also be provided. (For selecting timepoints: 1 month = 30 days, 1 year = 365 days.)

A listing of subjects who progressed based on the criteria defined above for CLL and SLL, and who died will be presented.

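### The PFS censoring rules in SAP 10.4 do not say that events take precedence, so a death before any response assessment can be coded as censored at first dose

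*SAP*

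**What the plan says.** SAP 10.4 measures PFS from the first dose of any study drug to progression or death from any cause. Protocol 10.6 uses the same definition and has no rule for unassessed subjects.

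Two censoring sentences follow in SAP 10.4. The first is limited to subjects without an event: "A subject who has neither progressed nor died will be censored on the date of his or her last adequate tumor response assessment". The second has no such limit: "Subjects without adequate baseline or post-baseline efficacy assessments will be censored on their first dose dates".

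Table 5 then lists six situations and states no order among them:

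- Row 1, "No post-baseline response assessments": censored at treatment start.
- Row 2, "Progression documented before subsequent anti-CLL/SLL therapy": event.
- Row 3, "Death before first PD and subsequent anti-CLL/SLL therapy": event at the date of death.
- Row 4, neither progression nor death: censored at the last adequate assessment.
- Row 5, "Study discontinuation for reasons other than PD or death": censored at the last adequate assessment.
- Row 6, "New anti-CLL/SLL treatment started with no claim of progression": censored at the last adequate assessment before the new treatment.

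PFS is analysed in the Safety and the Efficacy Evaluable (EE) populations (SAP 5.2). It is reported by dose cohort and overall within arm, with event counts and rates from three months onward. In addition, "Median and 1st quartile PFS will be estimated using Kaplan-Meier estimates".

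**The concern.** Take a subject who receives study drug and dies before any response assessment, with no documented progression and no new therapy. Row 1 and the unconditional sentence censor this subject at first dose. Row 3 and the PFS definition make the same subject an event at death. A programmer working down Table 5 meets row 1 first.

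If row 1 wins, the subject leaves the risk set before any event time and the death vanishes from the PFS analysis. The resulting bias favours treatment. It also departs from the protocol's definition without being declared, because SAP Section 15 lists no change to PFS.

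The unconditional sentence has a second overlap. It also covers a missing adequate baseline, so a subject with documented progression but no adequate baseline meets both that sentence and row 2. Row 1 does not share this overlap.

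**Working it through.** **The rules applied to one subject** (death unassessed, no progression, no new therapy)

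| Rule | Result |
|---|---|
| PFS definition, SAP 10.4 and Protocol 10.6 | Event at death |
| Table 5 row 3 | Event at death; no prior assessment required |
| Unconditional sentence, SAP 10.4 | Censored at first dose |
| Table 5 row 1 | Censored at treatment start |

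Rows 4 and 5 exclude deaths in terms; row 1 does not. SAP 17.3 defines an adequate assessment but ranks nothing.

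**Who is exposed.** Protocol 6.2.7 sets response assessment every 3 cycles (+4 weeks/-1 week) and at End of Treatment. The first 3-cycle assessment falls nominally at Cycle 4 Day 1:

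- Arms A and B: 3 × 28 + 1 = Day 85.
- Arm C, whose Cycle 1 has 29 days: 29 + 2 × 28 + 1 = Day 86.

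The exposed deaths are mainly those before that point with no End of Treatment assessment. Protocol 6.1.4 treats the Day 1 examination of each cycle as part of response assessment. If that examination counts as adequate, the exposed period for the unconditional sentence ends at about Cycle 2 Day 1: Day 29 in Arms A and B, Day 30 in Arm C.

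**Which analysis is affected.** The Safety population needs only one dose of any study drug (SAP 5.2.1), so these subjects are in it. The EE population needs a post-baseline efficacy assessment (SAP 5.2.3), so it excludes them and does not restore the deaths.

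**Size.** The plan gives no PFS figure to reproduce and no early-death rate, so this is an illustration. Assume one such death among n subjects and no other event or censoring by Day 90 (SAP 10.4 takes 1 month as 30 days).

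- Death counted: S(90) = 1 − 1/n, Greenwood term 1/(n(n−1)), log-log 95% limits S^exp(±1.96·√term/|ln S|).
- Row 1 programmed: the subject leaves the risk set at Day 1, S(90) = 1, and no log-log interval can be computed.

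| n | S(90), death counted | 95% CI | S(90), row 1 programmed |
|---|---|---|---|
| 3 | 2/3 = 0.667 | 0.054 to 0.945 | 1.000 |
| 6 | 5/6 = 0.833 | 0.273 to 0.975 | 1.000 |
| 20 | 19/20 = 0.950 | 0.695 to 0.993 | 1.000 |

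The values of n reflect SAP 4.1: 3 to 6 subjects per fixed-dose cohort in Arms B and C, and about 20 in Arm A.

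With n = 6, that death and then one progression:

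- Death counted: (5/6)(4/5) = 0.667, term 1/30 + 1/20, CI 0.195 to 0.904.
- Row 1 programmed: 4/5 = 0.800, term 1/20, CI 0.204 to 0.969.

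**First quartile.** Taking it as the first time S is 0.75 or less, a counted death reaches it at once when 1 − 1/n ≤ 0.75. That holds for n = 3 (0.667) and n = 4 (0.75), but not for n = 5 (0.80) or n = 6 (0.833). With the death censored it is not reached at that point.

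**The case against.** The best answer is that the SAP's intent is clear. The definition includes death from any cause. The sentence just before the unconditional one is limited to subjects without an event. Row 3 is specific to death and requires no assessment. SAP 17.2 says outcome dates may be subject to endpoint-specific censoring rules when the outcome did not occur. These points do favour counting the death. None of them ranks the rows of Table 5, however. SAP 17.2 is permissive and only suggests an order, and rows 4 and 5 show that the authors excluded deaths expressly where they meant to.

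The n = 3 figure also needs a limit. Under the 3 + 3 rules, a death in the DLT window generally either counts as a DLT, which takes the cohort to 6, or makes the subject non-evaluable and replaced, which gives at least 4. Apart from a cohort stopped after two DLTs, n = 3 is realistic mainly for deaths between the end of that window (Day 28 + 28 = 56 in Arm B, Day 29 + 8 = 37 in Arm C) and about Day 85. The n = 4 quartile result sits exactly on 0.75 and depends on the quantile convention. The overlap with row 2 is remote, because Protocol 6.2.2 makes a screening CT mandatory. These limits stand.

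Finally, PFS is secondary and descriptive, Phase 2 will not proceed, and deaths are listed and tabulated, so a miscoded death could be noticed. That lowers the importance but does not remove the contradiction.

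**Conclusion.** The concern holds. SAP 10.4 contains a censoring rule that, applied as written, contradicts its own PFS definition for a death before any assessment, and nothing in either document says which rule wins. If it is programmed that way, Safety-population PFS is biased upward: in the illustration by 33 percentage points at three months with 3 subjects, 17 with 6 and 5 with 20. Those figures assume exactly one such death and no other event or censoring by Day 90. The true number is unknown and may be zero, in which case the two readings agree on deaths. The intervals are very wide either way, and no power or type I error is affected. The point is of modest importance but should be settled before database lock.

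**What to change.** State in SAP 10.4 that Table 5 rows 2 and 3 take precedence over the no-assessment rule. Limit the unconditional sentence and row 1 to subjects with no qualifying PFS event: no documented progression before subsequent anti-CLL/SLL therapy, and no death before both progression and such therapy. Add that a qualifying death is an event on its date whether or not any assessment exists.

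Keep row 1 for subjects with no post-baseline assessment who start new therapy and later die. They stay censored at first dose, because row 6 needs a last adequate assessment that they do not have.

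The cost is one clause in the text and one in Table 5, with no new data. Reported PFS may be slightly less favourable.
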